17.5 Safety and tolerability evaluation

17.5.1 Adverse events

AEs will be coded by System Organ Class (SOC) and PT, using the Medical Dictionary for Regulatory Activities (MedDRA).

AEs will be classified as pre-treatment AEs (PTAEs) and TEAEs, according to the period of occurrence, as follows:

- PTAEs: all AEs occurring from the signature of the informed consent to participate in the study up to the first T or R dose, including AEs occurring after P and before T or R in Part B
- TEAEs: all AEs occurring after the first dose of T or R

Individual PTAEs and TEAEs will be listed in subject data listings. No summary table will be provided for PTAEs. TEAEs will be summarized by treatment and overall. The number and percentage of subjects with any TEAE and the number of TEAEs will be tabulated by SOC and PT, seriousness, relationship to treatment and severity.

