10.1.2 Dose regimen

Part A of the study:

In cohort 1, 10 healthy volunteers (HV) will receive a dose of T as a one single 30-min IV infusion and additional 10 subjects will receive a single IV dose of undiluted R (defined as R_a) as a one single 30-min IV infusion, according to a parallel group design. In each of 3 consecutive cohorts (cohorts 2, 3 and 4), 10 healthy volunteers (HV) will receive a single IV dose of T at a predefined infusion duration and will be sequentially treated as 3 subgroups of 3, 3, and 4 subjects, respectively.

A staggered approach with decreasing infusion time duration will be applied, from cohort 1 to cohort 4, to the administration of T, as follows:

Cohort 1: 30 min

Cohort 2: 15 min

Cohort 3: 5 min

Cohort 4: 2 min

At the end of cohort 1 and of each subgroup of cohorts 2, 3 and 4, safety and tolerability results will be evaluated by the Investigator and the study Sponsor Medical Expert. Predefined stopping rules will be considered for deciding about continuing with the next cohort treatment and a shorter injection duration of T (see § 13.2). Predefined stopping rules are applicable for subjects treated with T. After cohort 1, if the injection duration of 30 min proves to be safe and well tolerated, 15 min injection duration will be tested in cohort 2. If the injection duration of 15 min proves to be safe and well-tolerated, 5 min injection duration will be tested in cohort 3. If the injection duration of 5 min proves to be safe and well tolerated, a 2 min injection will be tested in cohort 4. If the safety data obtained from a treated cohort receiving T are considered as not sufficient for taking a decision on the infusion duration de-escalation process, and if additional safety data are deemed necessary to allow such decision to be taken, the study Investigator and the Sponsor Medical Expert may decide to add additional subjects (up to a maximum of 4 subjects per cohort) to the 10 subjects of the treated cohort.

Part B of the study will follow a 2-way, cross-over randomized design and will include 40 subjects.

All the subjects will receive one single IV dose of P (placebo, as 0.9% NaCl solution for infusion) in period 1, at the infusion duration selected in study part A.

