17.1 Analysis Sets

17.1.1 *Definitions*

A subject will be defined as screened after the signature of the informed consent, regardless of the completion of all the screening procedures.

A subject will be defined as eligible if he/she meets all the inclusion/exclusion criteria. Otherwise, he/she will be defined as a screen failure.

A subject will be defined as enrolled in the study if he/she is included in the interventional phase of the study. The enrolment will be performed through a non-randomized or randomized inclusion in the study.

An eligible but not enrolled subject will be defined as a reserve.

- Enrolled set: all enrolled subjects. This analysis set will be used for demographic, baseline and background characteristics
- Safety set: all subjects who receive at least one dose of the IMPs, including partial administration. This analysis set will be used for the safety analyses
- PK set A: all enrolled subjects who fulfill the study protocol requirements in terms of T or R_a administration and have evaluable PK data readouts, with no major deviations that may affect the PK results. This analysis set will be used for the statistical analysis of the PK results of study Part A
- PK set B: all enrolled subjects who fulfill the study protocol requirements in terms of T and R administration and have evaluable PK data readouts for the planned treatment

comparisons, with no major deviations that may affect the PK results. This analysis set will be used for the statistical analysis of the PK results of study Part B

Each subject will be coded by the CRO Biometry Unit as valid or not valid for the Safety set, PK set A and PK set B. Subjects will be evaluated according to the treatment they actually receive.

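### Part B adverse events after placebo are classed as pre-treatment and left out of every summary table, so the AE tables lack the drug-free reference matched to T on volume and duration

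*Protocol*

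**What the plan says.** Section 17.5.1 splits adverse events at the first dose of T or R. Events up to that point are PTAEs, "including AEs occurring after P and before T or R in Part B". The other class is "TEAEs: all AEs occurring after the first dose of T or R". On reporting, "Individual PTAEs and TEAEs will be listed in subject data listings", but "No summary table will be provided for PTAEs". By contrast, "TEAEs will be summarized by treatment and overall", with counts and percentages by system organ class, preferred term, seriousness, relationship and severity.

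Elsewhere P is handled as a study treatment. Section 10.1.1.3 describes it as an IMP. Section 10.1.2 states: "All the subjects will receive one single IV dose of P (placebo, as 0.9% NaCl solution for infusion) in period 1", at the duration chosen in Part A. Section 10.1.2.1 gives the full 20 mL for both T and P. Section 17.1.1 defines the "Safety set: all subjects who receive at least one dose of the IMPs, including partial administration", and evaluates subjects by the treatment actually received.

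For general safety, the comparator named in sections 9.2.2, 16.1.2.2 and 16.3 is R. Placebo is named as comparator for the QT objective (9.2.2) and the placebo-corrected ECG endpoints (16.1.2.2, 17.5.7).

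**The concern.** Part B has to show how T behaves when 20 mL is injected at the shortest duration accepted in Part A. Some AEs may come from the procedure (injection speed and volume, cannulation, confinement) and some from fosnetupitant. An AE table with T and R columns cannot help tell these apart, because R differs from T in three respects at once. The P administration is drug-free, in the same subject, with the same volume and duration, and its AEs are already recorded. Section 17.5.1 nevertheless groups these events with screening events and rules out a summary.

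Local tolerability makes this more than a formality. Section 13.2 directs the Part A review to events in the injection arm, and section 8.4 names infusion site thrombosis among the most frequent drug-related TEAEs in earlier experience.

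The definitions also do not line up. A subject dosed only with P is treated for the Safety set but cannot have a TEAE. Likewise, section 14.3.3 makes clinically significant ECG abnormalities after screening AEs. One arising after P belongs to the placebo condition in the cardiac evaluation but is pre-treatment in the AE analysis.

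**Working it through.** There is no plan figure to reproduce here. The check sets the relevant sections side by side and then sizes the gap.

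**1. Which administration is matched to T?** (Sections 10.1.1, 10.1.2, 10.1.2.1)

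| | T | P | R |
|---|---|---|---|
| Volume given | 20 mL | 20 mL | 50 mL after dilution |
| Duration | selected in Part A | same as T | 30 min |
| Fosnetupitant | 235 mg | none | 235 mg |
| Palonosetron | none | none | 0.25 mg |
| Given to each subject | yes | yes | yes |
| Order | randomized with R | always first | randomized with T |
| In AE summary tables (17.5.1) | yes | no | yes |

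P differs from T in the product and in its fixed position. R differs in volume and palonosetron, and in duration if Part A selects less than 30 min.

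**2. When does treatment begin?** Safety-set membership begins with any IMP dose, so in Part B with P on Day 1 of period 1. The treatment-emergent period begins with the first T or R dose on Day 3. Between them lie about 48 h in which a subject is in the Safety set but every AE is pre-treatment. A placebo-only subject is possible: randomization is on Day -1, before P, and randomized subjects are not replaced (19.1.2).

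**3. How much observation is left out of the tables?** Up to 40 subjects × 1 placebo administration = 40 administrations, each followed for about 48 h. For a subject who completes Part B, that is one of three administrations.

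**4. Would a P column be empty?** The protocol gives no AE rate for saline, so the rate p per subject is an assumption. Assuming independent subjects, the probability of at least one subject with an AE among 40 is 1 − (1 − p)^40:

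- p = 2%: 1 − 0.98^40 = 0.55 (0.8 subjects expected)
- p = 5%: 1 − 0.95^40 = 0.87 (2 expected)
- p = 10%: 1 − 0.90^40 = 0.99 (4 expected)

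At 5% or above the column would probably hold something. At 2% it is close to an even chance.

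**5. Does the mismatch distort a percentage?** Only the overall column could be touched. One placebo-only subject makes the denominator 40 instead of 39, a factor of 39/40 = 0.975. If 8 subjects had a TEAE (illustrative), 8/39 = 20.5% becomes 8/40 = 20.0%.

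**The case against.** The case for leaving section 17.5.1 alone has substance.

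- **R is a within-subject control.** A reader might infer that P is Part B's only one. It is not: every subject receives T and R in randomized order, and the general safety objective and endpoint name R. The planned TEAE tables answer that objective, and no objective asks for T against P on AEs. This stands. What P alone supplies is a drug-free reference matched on volume and duration.
- **The placebo data are not lost.** A reader might infer that they are discarded. They are not: AEs after P are recorded and listed individually, and a count could be made from the listing. Vital signs are also measured after P and summarized descriptively. P keeps its role in the ECG analyses, which the AE classification does not affect. This stands. The gap is in the AE summaries.
- **P is a limited control.** It always comes first, is open label and is not randomized. It has about 48 h of follow-up, against about 10 days or more for T and R. Differences between T and P are confounded with order and first confinement, and a 48-h table matches the windows but does not remove the fixed order. This stands and limits the comparison to description.
- **The definitions can coexist.** A Safety-set member without a TEAE is ordinary. By-treatment results follow the treatment received, so nothing places a placebo-only subject in a T or R denominator. This largely stands. A reader might infer materially diluted percentages, but step 5 of the working shows about half a percentage point per such subject, in one column.

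None of this supports calling events after an IMP dose pre-treatment. Nor is the matter simply left open for the SAP, because the protocol itself excludes the summary.

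**Conclusion.** The point holds as a reporting weakness. As written, the AE tables omit the one drug-free administration matched to T on volume and duration, and the start of the treatment-emergent period does not match the Safety set.

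The size is up to 40 administrations of about 48 h each that appear only in listings. The denominator effect is negligible. No decision rule, primary endpoint, bioequivalence conclusion or QT analysis changes, and T versus R remains the planned safety comparison.

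The conclusion rests on the protocol text alone. Only the illustration of how often a P column would hold an event depends on assumed AE rates. A change is worthwhile because the data are already collected and the column helps in reading any injection-related events after T.

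**What to change.** In section 17.5.1:

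1. Define PTAEs as AEs from consent to the first IMP dose, P included in Part B. This aligns the treatment-emergent period with the Safety set.
2. Assign AEs with onset from the start of P to the first T or R dose to treatment P.
3. Add a descriptive P column beside T and R, with the subjects who received each treatment as its denominator.
4. Add a table of AEs in the first 48 h after each administration, or up to the next dose if sooner, so that the windows match.
5. State that P is always first, open label, not randomized and followed for only about 48 h, so the P column is descriptive and T versus R remains the planned comparison.

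The cost is protocol and SAP wording, one extra column and one extra table. No new data are needed. The risk is over-reading a fixed-order comparison, which item 5 addresses.

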17.5.2 Physical examination

Date of the physical examination, overall investigator's interpretation (as normal or abnormal and, if abnormal, clinically significant or not clinically significant) and clinically significant abnormalities (if any) will be listed.

17.5.3 Laboratory data

Date/time of samples collection, overall investigator's interpretation (as normal or abnormal and, if abnormal, clinically significant or not clinically significant) and clinically significant findings (if any) will be listed. All laboratory results will be listed and a table of all the abnormal values will be presented. The overall investigator's interpretation will be summarized using tables of frequency.

17.5.4 Vital signs

Vital signs values will be listed and summarized by descriptive statistics.

17.5.5 *Body weight*

Body weight values at screening and final visit/ETV will be listed and summarized by descriptive statistics.

17.5.6 *ECG for immediate safety*

Date/time of ECG recordings, overall investigator's interpretation (as normal or abnormal and, if abnormal, clinically significant or not clinically significant) and clinically significant abnormalities (if any) will be listed. The overall investigator's interpretation will be summarized using tables of frequency.

17.5.7 *Continuous ECG*

For the cardiac safety evaluation and further analyses, 10-sec triplicate ECGs will be extracted within a time window of 10 min preceding PK sampling and evaluated (§ 14.3).

The QT interval will be presented raw and after HR correction using the Fridericia formula as primary endpoint. ECG data will be listed and summarized highlighting differences from baseline for quantitative variables and frequencies of treatment emergent abnormalities. The number of QTc values above 450 ms, 480 ms and 500 ms at each evaluation timepoint will be tabulated, jointly with its change from baseline. Likewise, values differing by more than 30 ms from the baseline at each time point will be tabulated.

Data from Holter continuous recording will be assessed in blind by the provider (§ 7.5) according to a centralized procedure.

The primary analysis will be based on exposure response modeling of the relationship between netupitant and its metabolites M1, M2 and M3 and change-from-baseline QTcF (Δ QTcF) with the intent to exclude an effect >10 ms at clinically relevant plasma concentrations of netupitant, M1, M2 and M3.

In addition, the effect of netupitant on the placebo-corrected Δ QTcF, Δ HR, Δ PR, Δ QRS, Δ QT, and Δ QTcB ($\Delta\Delta$ QTcF, $\Delta\Delta$ HR, $\Delta\Delta$ PR, $\Delta\Delta$ QRS, $\Delta\Delta$ QT, and $\Delta\Delta$ QTcB) will be evaluated at each post-dose timepoint ('by timepoint' analysis) using the Intersection Union Test. An analysis of categorical outliers will be performed for changes in HR, PR, QRS, QT, QTcF, QTcB, T-wave morphology and U-wave presence.

See also § 16.3.1.

18 DEFINITION AND HANDLING OF AEs AND SAEs

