9.2 Objectives of Part B

9.2.1 *Primary objective*

The primary objective of the study Part B is to investigate the exposure equivalence of T, at the shortest injection duration defined as safe in Part A, and R, administered as a 30 min diluted infusion. The equivalence in exposure will be estimated in terms of extent of exposure to netupitant (AUC_{0-∞} and AUC_{0-t}).

9.2.2 *Secondary objectives*

The secondary objectives of the study Part B are:

- To characterize the PK profile in plasma of fosnetupitant, netupitant and netupitant metabolites M1, M2 and M3 after administration of T at the shortest injection duration defined as safe in Part A and R, administered as 30 min diluted infusion.
- To confirm the safety and tolerability of T administered at the shortest injection duration defined as safe in Part A in comparison to R, administered as a 30 min diluted infusion.
- To assess the effect of T on ECG parameters (HR, QT, QTcF, QTcB, PR and QRS intervals).
- To assess the effects of the administration of fosnetupitant on the QT interval in the shortest infusion time (defined in Part A) compared to placebo, in male and female healthy subjects.

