The assessment of T and R bioequivalence will be conducted on netupitant. The prodrug fosnetupitant is known to be promptly transformed into netupitant after the administration. Netupitant is the active species endowed with antiemetic efficacy in the delayed phase of emesis, defined as the period of time from 24 h after start of chemotherapy treatment onwards, up to 120 h after start of chemotherapy. Thirty (30) min after the end of the 30-min IV infusion in cancer patients, fosnetupitant mean plasma concentration was <1% of C_{max} . The prodrug was detectable until 2 to 4 h after the start of infusion (mean t_{last} 3.13 h). Netupitant peak concentrations were reached at the end of fosnetupitant infusion and netupitant exposure was appreciated for several days after IV administration with MRT and $t_{1/2}$ values of 162.6 h and 143.7 h, respectively (10).

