- On Day 13 of period 1 and Day 11 of period 2 (in period 2, coinciding with the final visit measurement)
- ETV

Triplicate 12-lead ECG parameters and abnormalities will be recorded in the individual CRFs.

14.3.2 *Continuous 12-lead ECG*

In Part B, on each dosing day, a continuous 12-lead ECG will be recorded and discrete triplicate recordings will be extracted from the continuous Holter ECG monitoring for the data analysis.

Continuous 12-lead ECG will be recorded:

- On Day 1 period 1, from 1 h before to 48 h after the end of the infusion. In addition, discrete triplicate 12-lead ECGs will be extracted 3 times within 1 h before the start of infusion and at the end of the infusion and 0.5, 1, 2, 4 and 24 h after the end of the infusion
- On Day 3 of period 1 and on Day 1 of period 2, from shortly before the injection/infusion start to 48 h after the end of the infusion/infusion. In addition, discrete triplicate 12-lead ECGs will be extracted at pre-dose 3 times within 1 h before the start of the injection/infusion and at the end of the injection/infusion and 0.5, 1, 2, 4, 24 and 48 h after the end of the injection/infusion

ECG continuous recording will be performed using appropriate continuous 12-lead recording devices with the capacity for digital signal processing, adequately serviced and calibrated. For the ECG monitoring, the operator will always apply the same technique for skin preparation, lead placement and time of recording. Subjects will rest quietly in a fully supine position for at least 10 min before each scheduled timepoint for ECG evaluation. The provider (§ 7.5) will be in charge to provide the devices for continuous monitoring, to train the Phase I Unit personnel in the use of the device, to extract and to analyze the data. Triplicate 10-sec ECGs will be extracted within a time window of 10 min preceding coinciding PK sampling.

ECG tracings will be electronically stored and sent to the central ECG laboratory for analysis at the end of each period.

14.3.3 *Tolerance ranges for ECG recording*

Actual ECG recording times will be recorded in the individual CRFs. The actual times of recordings should not exceed the recommended tolerance ranges presented in the following table. Any deviation outside the recommended ranges, only in study Part A, will be verified through Data Clarification Forms and, if confirmed, will be reported as protocol deviation.

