14.5 Sampling for pharmacokinetic analysis

14.5.1 Venous blood sampling

Venous blood samples will be collected from a forearm vein through an indwelling catheter or venipuncture at the times summarized in the following table. All blood samples will be withdrawn from the contralateral arm with respect to the arm used for the injection/infusion. The indwelling catheter will be removed at the end of the confinement or before in case of need.

Table 14.5.1.1 Schedule of PK blood sampling

		Blood sampling times after the start of T or R treatment									
		T injection of						Reference product infusion of			
		2 min		5 min		15 min		30 min		30 min	30 min
		Part A	Part B	Part A	Part B	Part A	Part B	Part A	Part B	Part A (Ra)	Part B (R)
Pre-dose	X	X		X	X	X	X	X	X	X	X
2 min	X	X									
5 min	X	X	X	X							
10 min	X	X	X	X							
15 min	X	X	X	X	X	X					
20 min	X	X	X	X	X	X					
30 min	X	X	X	X	X	X	X	X	X	X	X
45 min	X	X	X	X	X	X	X	X	X	X	X
1 h	X	X	X	X	X	X	X	X	X	X	X
1.5 h	X	X	X	X	X	X	X	X	X	X	X
2 h	X	X	X	X	X	X	X	X	X	X	X

		Blood sampling times after the start of T or R treatment									
		T injection of								Reference product infusion of	
		2 min		5 min		15 min		30 min		30 min	30 min
		Part A	Part B	Part A	Part B	Part A	Part B	Part A	Part B	Part A (Ra)	Part B (R)
3 h	X	X	X	X	X	X	X	X	X	X	X
4 h	X	X	X	X	X	X	X	X	X	X	X
8 h	X	X	X	X	X	X	X	X	X	X	X
12 h	X	X	X	X	X	X	X	X	X	X	X
24 h	X	X	X	X	X	X	X	X	X	X	X
48 h		X		X		X		X			X
72 h		X		X		X		X			X
96 h		X		X		X		X			X
120 h		X		X		X		X			X
144 h		X		X		X		X			X
168 h		X		X		X		X			X
192 h		X		X		X		X			X
216 h		X		X		X		X			X
240 h		X		X		X		X			X

T = Fosnetupitant 235 mg in 20 mL IV injectable solution administered at predefined time durations (30, 15, 5 and 2 min);

R = Fosnetupitant/palonosetron 235 mg/0.25 mg (IV Akynezo FDC) 20 mL liquid formulation diluted to 50 mL and administered in 30 min (Part B);

Ra = Fosnetupitant/palonosetron 235 mg/0.25 mg (IV Akynezo FDC) 20 mL liquid formulation, undiluted and administered in 30 min (Part A).

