All the scheduled samples will be collected at the given times counted from the start of the injection/infusion. However, if, for whatever reason, a premature interruption of injection/infusion is needed or if a duration longer than that initially scheduled is needed, the sampling scheduled at the end of injection/infusion is to be moved to the actual end time. Actual sampling times for each subject will be recorded in the individual CRFs. The actual sampling times should not exceed the recommended tolerance ranges presented in the following table. Any deviation outside the recommended ranges will be verified through Data Clarification Forms and, if confirmed, will be reported as protocol deviation, although it will not automatically lead to the exclusion of the concerned subjects from the PK Sets.

Table 14.5.1.2 Tolerance ranges for the scheduled blood sampling times for PK analysis

Sampling time	Tolerance range
Pre-dose (0)	Within 30 min before T or R treatment administration
2 min, 5 min, 10 min, 15 min, 20 min, 30 min	0 min
45 min, 1 h, 1.5 h, 2 h	± 2 min
3 h, 4 h, 8 h, 12 h, 24 h	± 5 min
48 h, 72 h, 96 h, 120 h, 144 h, 168 h, 192 h, 216 h, 240 h	± 60 min

Actual sampling times for each volunteer will be recorded in the individual CRFs.

Blood samples (6 mL each) for PK analysis will be collected using an indwelling catheter with switch valve during confinement. The indwelling catheter for blood collection will be placed on the contralateral arm with respect to the infusion arm. The cannula will be rinsed, after each sampling, with about 1 mL of sterile saline solution containing 20 I.U./mL Na-heparin. The first 1.5 mL of blood will be discarded at each collection time to wash the cannula out of saline

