solution and avoid diluting the analyte concentrations. The remaining volume of 4.5 mL of blood will then be collected from the catheter and transferred with a syringe into K₂EDTA tubes. Blood samples will be immediately centrifuged at 1500 g for 15 min at 4° C to obtain plasma. If immediate centrifugation is not possible, blood samples will be kept on melting ice or in a refrigerator at 4° C for a maximum of 1 h. Each plasma sample will be divided at room temperature within a maximum of 4 h from blood centrifugation into 6 pre-labeled tubes: F1 and F2 (both of at least 200 µL) for the assay of fosnetupitant, N1 and N2 (both of at least 500 µL) for the assay of netupitant and its metabolites. For the collection of the 3rd aliquots (F3 and N3), the remaining plasma will be used. Plasma samples will be stored frozen at ≤-70° C (F and N aliquots) until analysis.

If any clinical assessment, such as vital sign measurement or ECG recording, is foreseen at the same time-point as blood sampling for PK analysis, blood collection will be performed at the scheduled time. Vital signs and ECG recordings for immediate safety evaluation can be performed before the pre-dose sampling and after the post-dose samplings, but inside the recommended tolerance ranges presented in [Table 14.2.1](#) and [Table 14.3.1](#). Any deviations outside the recommended time ranges will be verified through Data Clarification Forms and reported as a protocol deviation. Discrete ECGs will be extracted from the continuous monitoring by the provider before blood sampling scheduled at the same time point.

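### For a 2- or 5-min injection, the Part B rule for extracting the end-of-injection ECG lets pre-dose recordings count as post-dose

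*Protocol*

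**What the plan says.** One of the QT objectives of Part B (Protocol 9.2.2) is "To assess the effects of the administration of fosnetupitant on the QT interval in the shortest infusion time", compared with placebo. Section 17.5.7 sets out two analyses for it. On the first it says "The primary analysis will be based on exposure response modeling of the relationship between netupitant and its metabolites M1, M2 and M3" and change from baseline in QTcF. The second is a placebo-corrected comparison at each post-dose timepoint with an intersection-union test.

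The timing rules that feed both analyses are spread over several sections:

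- **ECG times (14.3.2; Table 4.2, note 9).** On T and R days, ECGs are extracted "3 times within 1 h before the start of the injection/infusion and at the end of the injection/infusion", then at 0.5, 1, 2, 4, 24 and 48 h after the end.
- **Extraction window (14.3.2, repeated in 17.5.7).** "Triplicate 10-sec ECGs will be extracted within a time window of 10 min preceding coinciding PK sampling".
- **Order (14.5.1).** "Discrete ECGs will be extracted from the continuous monitoring by the provider before blood sampling scheduled at the same time point".
- **Blood-sampling clock (Table 14.5.1.1).** The column heading is "Blood sampling times after the start of T or R treatment", so the end-of-injection sample falls at 2, 5, 15 or 30 min, according to the duration selected.
- **Sampling tolerance (Table 14.5.1.2).** The row "2 min, 5 min, 10 min, 15 min, 20 min, 30 min" allows 0 min.
- **Deviations (14.3.3).** Actual ECG times in Part B are recorded, but departures from schedule are not reported.

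**The concern.** A 10-min look-back works when the infusion lasts at least 10 min. For a shorter injection it reaches back past the start of dosing. The protocol makes no exception for this, although Part A is designed to find the shortest tolerable duration and may select 5 or 2 min.

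The timepoint affected matters for the prodrug. Section 8.2.1.1 reports that fosnetupitant peaks mainly at the end of infusion. Section 11.2 reports that, 30 min after the end of a 30-min infusion in cancer patients, "fosnetupitant mean plasma concentration was <1% of" Cmax. The next ECG extraction is 0.5 h after the end. If the end-of-injection ECG is partly pre-dose, no other planned Part B extraction on the T day covers the peak. The T-versus-placebo comparison could then be diluted at the one time when a short-lived prodrug effect would show.

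**Working it through.** **Step 1: the window.** Let T be the injection duration in minutes. The sample is at T from the start with 0 min tolerance, and the ECGs come from the preceding 10 min. The window is therefore (T - 10) to T, and the pre-dose share is max(0, 10 - T)/10.

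| T (min) | Window from start of dosing (min) | Pre-dose share | Overlap with the 1-h baseline window |
|---|---|---|---|
| 2 | -8 to +2 | 8/10 = 80% | 8 min |
| 5 | -5 to +5 | 5/10 = 50% | 5 min |
| 15 | +5 to +15 | 0% | none |
| 30 | +20 to +30 | 0% | none |

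**Step 2: the conflict.** A recording at -6 min before a 2-min injection satisfies the look-back rule and the ECG-before-blood rule. It does not satisfy the end-of-injection label in 14.3.2 or the post-dose label in 17.5.7. The same tracing would also be eligible as baseline.

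**Step 3: the placebo day.** Table 14.5.1.1 covers T and R only, and Table 4.2 marks no PK sampling on Days 1-2 of period 1. With no coinciding sample, the look-back rule has nothing to attach to, and only the nominal end of infusion applies. As written, the T window and the placebo window can differ.

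**Step 4: possible dilution.** The assumptions, none of them from the protocol, are that the tracings are spread evenly over the written window, that the effect is proportional to prodrug concentration without lag, and that kinetics are one-compartment with constant-rate input. During injection the concentration relative to its end value is (1 - exp(-kt))/(1 - exp(-kT)), and it is zero before dosing. Averaged over the 10-min window, the share of the end-of-injection effect that is seen is

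f = [T - (1 - exp(-kT))/k] / [10 (1 - exp(-kT))].

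- Slow elimination (k near 0): f = T/20, which is 10% for T = 2 and 25% for T = 5. The 0.956-h half-life reported in 8.2.1.1 for 260 mg is close to this limit.
- Level of 1% at 30 min (from 11.2): k = ln(100)/30 = 0.1535 per min, a half-life of 4.5 min. For T = 2, f = (2 - 0.2644/0.1535)/(10 x 0.2644) = 10.5%. For T = 5, f = (5 - 0.5358/0.1535)/(10 x 0.5358) = 28%.
- Level of 0.1% at 30 min (half-life about 3 min): 10.8% and 29.7%.

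The half-life hardly matters. The result is about 10% for 2 min and 25-30% for 5 min.

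**Step 5: what a better window recovers, on the same assumptions.** Dropping pre-dose tracings but spreading the rest over the whole injection multiplies f by 10/T. This gives 50-54% (2 min) and 50-59% (5 min). Tracings from the last 30 s before the end would see about 87-90% and 95-97%.

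**The case against.** The best defence is to read the sections together. Pre-dose extractions are listed separately, the timepoint is named as the end of the injection, and the analysis is confined to post-dose times. Ten minutes is then an outer limit, and a sensible ECG laboratory would not take a tracing from before the injection. Actual times are recorded. On the placebo day the nominal time is clear enough. The matter is secondary, arises only for 2 or 5 min, and Part A records end-of-injection ECGs with a tolerance of +10 min, hence after dosing.

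Much of this stands. It shows that the wrong extraction is not forced. It does not remove the conflict, because the look-back rule appears twice without exception and Part B timing departures are not reported. Part A has about 10 subjects per T cohort and no placebo.

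A reader might infer more: that leaving fosnetupitant out of the primary exposure-response model is an error. The protocol does not support that. It gives reasons for focusing on netupitant: the pharmacology is mainly attributable to it (8.1), conversion is rapid with limited prodrug exposure (8.2.1), and it is the active species (11.2). Section 17.5.7 already confines the 10 ms exclusion to netupitant, M1, M2 and M3. The by-timepoint comparison with placebo does not depend on which analyte is modelled, so it addresses the 9.2.2 objective once its timing is sound.

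**Conclusion.** The extraction rule conflicts with the ECG schedule for injections shorter than 10 min. If 2 or 5 min is selected, 80% or 50% of the permitted window for the end-of-injection ECG precedes dosing. That part is arithmetic on the stated rules and needs no assumption. The dilution to about 10% or 25-30% is illustrative: it rests on even spread, proportionality without lag and one-compartment kinetics, whereas 8.2.1.1 describes bi-exponential decline. The figure of less than 1% comes from cancer patients after a 30-min infusion.

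Two further inferences should be avoided. The protocol reports no prodrug QT signal, and 8.4 describes a low QT risk from data so far, so this is not evidence of a hazard. Nor can one say that a given QT effect would pass or fail the test, since the protocol states neither an effect size nor a QTcF variance. The point is a correctable timing rule for a secondary objective and should be settled before Part B recordings are extracted.

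**What to change.** In 14.3.2 and 17.5.7, reconcile the passages for the end-of-injection timepoint. Define its extraction window relative to the end of the injection, as close to it as is workable and still before the blood draw. Exclude any recording from before the start of dosing. Apply the same window on the placebo day, where no PK sample is scheduled. The other timepoints can keep the 10-min look-back.

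The cost is a change of wording on recordings already planned. The drawback is that the window is short for a 2-min injection and may miss an effect that lags the peak; the 0.5 h extraction remains for later effects.

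Optionally, and not as correction of an error, a supportive fosnetupitant concentration-QTcF model could be fitted from samples already assayed. It would rest on essentially one informative ECG time, so its estimate may be imprecise, and it would need the corrected window to be meaningful.
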